5.7.4. Loop-mediated isothermal amplification (LAMP)
5.8. Statistical Analysis Plan20
5.9. Data analysis and interpretation
5.10. Benefits and beneficiaries of the proposed study22
5.11. Dissemination of findings
5.12. Ethical Considerations
6.0. WORK PLAN
7.0 English Version of Questionnaire2
8.0 References

SUMMARY

Background: Malaria is one of the major public health problems in sub-Saharan Africa. It contributes significantly to maternal and fetal morbidity and mortality in affected countries.

Objective: The aim of this study is to evaluate the impact of enhanced case detection using molecular testing (LAMP) on maternal and infant morbidity and mortality in a prospective study design.

Method: A pragmatic randomized control diagnostic trial will be conducted from October 2020 until October 2021 in pregnant mothers at sites in Ethiopia. Both symptomatic and asymptomatic first and early second trimester pregnant women will be included in the study and individually randomized to either standard of care or enhanced cased detection arms using LAMP for malaria. Women (n=2583) will be enrolled during a twelve-months period encompassing the peak transmission seasons and then followed until delivery. In the standard of care arm, venous blood sample will be collected from each study participant and the presence of *Plasmodium* infection will be diagnosed by microscopy in symptomatic patients. Pregnant women who test positive for malaria will be referred and treated for malaria with quinine or artemisinin combination therapies (ACTs) as per national guidelines. In the intervention arm, mothers who are symptomatic or asymptomatic will be tested by a commercially available CE-approved LAMP malaria test and microscopy/RDT for malaria at each clinic visit and treated if positive by any test. Pregnant mothers who require treatment will be referred and treated with either quinine or artemisinin combination therapy (ACTs) as per national guidelines. The primary outcome is the proportion of deliveries with low birth weight based on WHO definition, with secondary outcomes of:(i)absolute birth weight; (ii) maternal hemoglobin;(ii) neonatal hemoglobin at birth;(iv) neonatal mortality; (v) stillbirth; and (vi) prematurity in each arm of the study.

Result Dissemination plan: The results of this study will be presented at national and international scientific conferences. It will also be published in a reputable journal.

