symptomatic and asymptomatic first and second trimester mothers will be included in the study and individually randomized to one of two arms: standard of care or enhanced cased detection arms using LAMP for malaria. Mothers will be enrolled during a twelve-months period from October 2020 to October 2021 and then followed until 28 days after delivery. Given the rate of pregnant mothers at the locations, we anticipate that the required minimum of 2583 mothers will be enrolled in the study during the study period. In the first standard of care arm, venous blood sample will be collected from each study participant and the presence of *Plasmodium* infection will be diagnosed by microscopy in symptomatic patients. Pregnant women who test positive for malaria will be referred and treated for malaria with quinine or ACTs as per national guidelines. In the second (test) arm, mothers whether symptomatic or asymptomatic will be tested by a commercially available CE-approved LAMP malaria test (Meridien Biosciences, Illumigene Malaria M kit, Cincinatti, USA) and Human Diagnostics LoopAMP (Wiesbaden, Germany) at each clinic visit in addition to RDT/microscopy. The commercial LAMP tests can distinguish P. falciparum and P. vivax and treatment will be given according to national guidelines. The purpose of doing all tests in the intervention arm is to determine how many additional cases LAMP identified. The primary outcome is the proportion of deliveries with low birth weight, with secondary outcomes of: (i) absolute birth weight; (ii) maternal hemoglobin; (ii) neonatal hemoglobin at birth (Standard Hgb testing from peripheral blood or finger prick); (iv) neonatal mortality; (v) stillbirth; and (vi) prematurity in each of the two arms. Additionally, signs of current or past *Plasmodium* sequestration in the placenta will be evaluated.

[figure not shown]

Figure 1: Flowchart summarizing randomized trial

There will be a total of at least five antenatal visits (mandatory). Emergencies (medical consultation outside the planned visit) will be recorded for each included woman. Visit 1 and 2 may be combined for mothers who present in the second trimester. The following table summarizes the procedures to be conducted at each visit.

Visit #	Time frame	Aim	Action for the study
1	Visit at health care center	Inclusion	Enrolment and randomisation
2	26 weeks gestation	Follow up	Malaria testing as per inclusion arm (2mL venous blood on EDTA) +ANC regular care Maternal Hgb

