5.8. Statistical Analysis Plan

Raw data will be entered in SPSS version 20 software and analyzed using STATA version 13. Mothers with twins will be excluded from the analysis of birth outcomes. The sensitivity, specificity and predictive values will be calculated for microscopy and LAMP versus a gold standard of PCR. Statistical analysis of epidemiological variables and malaria positivity will be determined using univariate binomial regression. Variables found to be statistically significant with initial analysis will then characterized through multivariate analysis regression analysis. Risk ratios for primary outcome variables for intervention against standard of care arm will be calculated. Subgroup analysis will be done for potential confounders, and to compare positivity by LAMP and microscopy in the intervention arm.

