Primary objective:

The primary objective of this trial is to evaluate the effectiveness of LAMP-based enhanced malaria detection in improving pregnancy outcomes as measured by birth weight, neonatal anemia, maternal anemia, and stillbirth.

Secondary objective:

The secondary objectives are:

- a. To determine the proportion of asymptomatic MiP cases revealed by microscopy, RDT and LAMP
- b. To evaluate the impact of the intervention in terms of malaria-associated placental damage as evaluated by placenta weight and placental malaria.
- c. To evaluate the performances of IllucidX LAMP(ultrasensitive) compared to the approved method using the samples from the trial.
- d. To compare the diagnostic performance of microscopy, RDT and LAMP against qRT-PCR in MiP.
- e. To decipher parasitic genotypes that may impair diagnostic test performances and treatment efficacy using parasite whole-genome sequencing.

Section 3: Trial Methods

1. Trial design

The study is a prospective diagnostic study of malaria in pregnant women. The goal is to determine whether: (i) LAMP provides a clinically measurable benefit compared to current first-line diagnostic test of Giemsastained microscopy and whether (ii) enhanced case detection of asymptomatic mothers with LAMP has added value in terms of outcomes. We hypothesize that addition of LAMP to one arm will be of greater benefit than microscopy alone due to additional LAMP sensitivity. We further hypothesize that enhanced case detection by screening asymptomatic mothers at each antenatal visit will be of additional value in treating malaria. Both symptomatic and asymptomatic first and second trimester mothers will be included in the study and individually randomized to one of two arms: standard of care or enhanced cased detection arms using LAMP for malaria. Mothers will be enrolled during a twelve-months period from March 2021 to July 2022 then followed until 28 days after delivery

2. Randomization

Women will be screened for eligibility and randomized either in the Standard of Care (SOC, 1/3 of included women) arm or in the intervention arm (2/3 of included women).

Randomization will be implemented at each health center. Stratification per parity (primiparus, second pregnancy and \geq 3 pregnancy) will be implemented to avoid confounding factor of acquired immunity for MiP variants.

3. Sample size

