The sample size calculation for this study is based on detecting a difference in the proportion of deliveries with a low birth weight (LBW), which was felt to be the most clinically important outcome variable. The prevalence of deliveries with a LBW in Ethiopia was estimated to be 17.3%. An alpha of 0.05 was selected with an allocation ratio of 3:1 in favor of the enhanced case detection arm. The study will be powered to detect an absolute difference in the proportion of deliveries with a LBW of 5%, so a proportion in the enhanced case detection arm of 12.3% compared to 17.3% in the standard of care arm. Using a continuity correction and an attrition rate of 20%, a total sample size of 2583 is required to achieve 80% power.

4. Framework

The LAMPREG trial aims to show the superiority of the intervention arm.

5. Statistical Interim analyses and stopping guidance

a. Two formal interim analysis are planned

- One formal statistical interim analysis is planned when 25% of the total inclusion target number (n = 646) is reached. This interim analysis will focus on the inclusion baseline data and the follow-up data available to date.
- Another formal statistical interim analysis is planed when 25% of the inclusion target reached the end of the protocol (28 days post-natal delivery). This analysis will be partial since post hoc gold standard molecular testing will not be available yet.
 - b. Adjustments planned of the significance level due to interim analysis

The prevalence of malaria in the study sites is paramount for the study outcome. Interim analysis will tailor this factor and decision of site closure or site initiation may be taken.

c. Details of guidelines for stopping the trial early

The LAMPREG trial interim results will be presented to an advisory board. LAMPREG is not a new interventional drug trial, and therefore unlikely to be subject to study termination. The Ethiopian NRERC ethical board waived the need of independent data monitoring and safety committee for LAMPREG.

6. Timing of final analysis

The final analysis of clinical data in the SOC *vs.* LAMP arm will be performed after the last follow up is completed, in a time frame of 6 months (secund semester of 2022), given that data entry is performed according to the protocol.

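### The total of 2583 is not what 80% power with 20% attrition requires: at 3:1 it covers only 16.7% loss (2690 needed), and at the SAP's other ratio, 2:1, 2295 would suffice

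*SAP*

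**What the plan says.** SAP Section 3.3 and protocol 5.6 give the same calculation. It is built on the primary outcome, the proportion of deliveries with low birth weight, "so a proportion in the enhanced case detection arm of 12.3% compared to 17.3% in the standard of care arm", with alpha 0.05 and 3:1 allocation in favour of enhanced case detection. It ends: "Using a continuity correction and an attrition rate of 20%, a total sample size of 2583 is required to achieve 80% power". SAP Section 4.1 makes all tests two-sided at 5%. Neither document gives the evaluable number before attrition or says how the 20% was applied.

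The total is used elsewhere as a firm requirement:

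- Protocol Summary: "Women (n=2583) will be enrolled during a twelve-months period".
- Protocol 5.2: "we anticipate that the required minimum of 2583 mothers will be enrolled in the study during the study period".
- SAP Section 3.5 sets the first interim analysis when "25% of the total inclusion target number (n = 646) is reached".

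SAP Section 3.2, immediately before the sample size section, describes a different allocation. Women are "randomized either in the Standard of Care (SOC, 1/3 of included women) arm or in the intervention arm (2/3 of included women"), which is 2:1.

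**The concern.** An attrition rate of 20% means that one randomised woman in five has no usable outcome. The number to randomise is then the evaluable number divided by 0.8. Multiplying by 1.2 gives a smaller total that tolerates less loss. The loss matters here because SAP Section 6.3 does not impute outcomes, so a woman without a recorded birth weight drops out of the comparison.

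The ratio conflict in the SAP compounds the problem, because the required total depends on the ratio. Anyone who repeats the calculation will not obtain 2583. If losses reach 20% or accrual falls short, the sponsor would also lack a true statement of what 2583 delivers. At stake are the accuracy of the planning statement and the enrolment target built on it. This is not evidence that the trial is materially underpowered.

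**Working it through.** **Inputs.** p1 = 0.173 (standard of care), p2 = 0.123 (intervention), d = 0.05, 80% power, continuity correction, 20% attrition and ratio k = 3 (SAP 3.3, protocol 5.6); two-sided 5% (SAP 4.1); k = 2 as the alternative (SAP 3.2). z values are 1.960 and 0.8416.

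**Formula.** With p̄ = (p1 + k·p2)/(1 + k), the standard-of-care arm needs

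n = [1.960·√(p̄(1−p̄)(1+1/k)) + 0.8416·√(p1(1−p1) + p2(1−p2)/k)]² / d²

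and, with the continuity correction,

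n_c = (n/4)·[1 + √(1 + 2(k+1)/(k·n·d))]².

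**At 3:1, reproducing the plan's figure.**

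- p̄ = 0.1355; n = (1.960 × 0.39520 + 0.8416 × 0.42312)² / 0.0025 = 511.4.
- n_c = (511.38/4) × [1 + √(1 + 8/76.71)]² = 537.7, so 538.
- Evaluable: 538 + 3 × 538 = 538 + 1614 = 2152.
- 2152 × 1.2 = 2582.4, rounded up to **2583**, the stated total.
- 2152 / 0.8 = **2690**, the number that leaves 2152 after a 20% loss.
- Shortfall: 2690 − 2583 = 107, which is 4.1% of 2583.
- Loss that 2583 can absorb: 1 − 2152/2583 = 16.7%.
- 20% loss from 2583 leaves 2583 × 0.8 = 2066, which is 86 below 2152.

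**At 2:1, same method.**

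- p̄ = 0.13967; n = (1.960 × 0.42455 + 0.8416 × 0.44385)² / 0.0025 = 581.4; n_c = 611.1, so 612.
- Evaluable: 612 × 3 = 1836; 1836 / 0.8 = **2295**; 1836 × 1.2 = 2203.2.
- 2583 − 2295 = 288 more than required.

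**Other routes to 2583, each divided by 0.8.**

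| Variant | Total |
|---|---|
| 3:1, no continuity correction | 2560 |
| 3:1, arcsine, no correction | about 2622 |
| 3:1, unpooled variance, corrected | about 2942 |
| 3:1, one-sided, corrected | 2160 |
| 2:1, no continuity correction | 2183 |
| 1:1, corrected | 2078 |

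None gives 2583. The two nearest, 2560 and 2622, leave out the correction that the text says was used.

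**Power of 2583 with 20% lost (2066 evaluable).** Let s0 and s1 be the standard errors of the difference under the null and the alternative, and c = ½(1/n1 + 1/n2). Corrected power is Φ[(d − c − 1.960·s0)/s1]; uncorrected power omits c.

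- 3:1 (about 517 + 1549): s0 = 0.01739, s1 = 0.01862, c = 0.00129. Corrected: (0.05 − 0.00129 − 0.03408)/0.01862 = 0.786, power 78.4%. Uncorrected: 0.855, power 80.4%.
- 2:1 (about 689 + 1377): s0 = 0.01618, s1 = 0.01691, c = 0.00109. Corrected: 1.017, power 84.6%. Uncorrected: 1.082, power 86.0%.

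Protocol 5.8 says: "Risk ratios for primary outcome variables for intervention against standard of care arm will be calculated". A Wald test on the log risk ratio, simulated 400,000 times per case, has power 80.9% at 3:1 and 86.2% at 2:1.

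**The case against.** The arithmetic itself is hard to dispute. The case on the other side concerns weight and framing.

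- **The figure is recovered exactly once 20% is added, so only the last step is at fault, and that step is inferred.** This is fair as to how 2583 arose. The conclusion does not depend on it: however 2583 was reached, the stated inputs do not require it.
- **The analysis loses no power below 80%.** This stands. Neither document plans a continuity-corrected final test; the correction appears only in the sample size sentence. With 20% lost at 3:1, an uncorrected test has 80.4% power and the log risk ratio test 80.9%. The uncorrected requirement at 3:1 is 2560, below 2583. What remains is a wrong stated figure, with a gap of 1.6 points under the formula the plan chose.
- **At 2:1 there is a surplus, so the shortfall depends on an unresolved conflict.** This is correct, and it is why the ratio must be settled first. The sentence would still be wrong, because 2583 would not be the number required for 80% power.
- **The SAP cites protocol version 1.5, while the protocol reviewed is version 1.1.** Version 1.5 may read differently, so it should be checked before the protocol is edited. This does not rescue the SAP, which contains both ratios itself.
- **Protocol 5.8 excludes mothers with twins from the birth outcome analysis, and it is not said whether the 20% includes them.** This is a valid gap. It changes no figure above, but the revised sentence should say what the 20% covers.

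**Conclusion.** The concern holds. Under the stated inputs 2583 is not the total required for 80% power with 20% attrition: 2690 is needed at 3:1 and 2295 at 2:1. At 3:1, 2583 protects against 16.7% loss. With 20% loss it gives 78.4% power under the continuity-corrected planning formula, and 84.6% at 2:1.

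The size is small, and nothing here shows that the planned comparison has less than 80% power. The result rests on the pooled-variance two-proportion formula with continuity correction (which recovers 2583 exactly when 20% is added), on attrition meaning the share of randomised women without a usable birth weight, and on equal loss in the two arms. The correction should be made because the documents rely on the figure as a requirement and it is wrong at either ratio.

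**What to change.** First reconcile the allocation ratio: 3:1 in SAP 3.3 and protocol 5.6, 2:1 in SAP 3.2. Then restate the sentence in both documents, after checking the protocol version the SAP cites, and say whether the 20% includes twin pregnancies.

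- **If 3:1:** state that 2583 randomised gives 78% power with 20% attrition under the continuity-corrected formula (80% if attrition is at most 16.7%; about 80% with 20% attrition for an uncorrected test). Alternatively, give 2690 as the requirement.
- **If 2:1:** state that 2583 randomised gives about 85% power with 20% attrition under the continuity-corrected formula, and that 2295 are required for 80%.

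The cost is one sentence in each document. If 2583 is kept, enrolment and the interim trigger of 646 (0.25 × 2583 = 645.75) do not change. If the total changes, the trigger moves with it: 0.25 × 2690 = 672.5, so 673; or 0.25 × 2295 = 573.75, so 574. The references to 2583 in the protocol Summary and Section 5.2 would need the same edit, and describing it there as the required minimum should be corrected in any case.

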The laboratory testing post trial (gold standard testing, parasitic variant assessment) is scheduled for 2 years post sample collection, with analysis and publication of results within a 3-year frame (end of 2022- first semester of 2023).

7. Timing of outcome assessments

The scheduled of ANC visit is given in the study protocol (v1.5 – see table 5).

Section 4: Statistical Principles

1. Confidence intervals and p-values

All applicable statistical tests will be two-sided and will be performed using a 5% significance level.

All confidence intervals presented will be 95% and two-sided.

2. Adherence and Protocol Deviations

Protocol adherence is defined by the completion of all ANC visit as per study arm (included treatment course completion for women eligible) and the follow-up of the newborn for 28 days post-delivery.

Nonadherence is defined by the number of missed visits, the loss to follow-up or the absence of recorded birth weight.

Protocol deviation is defined as:

- Non-administration of malaria treatment for LAMP positive women in the intervention arm
- Incomplete treatment administration for any treated women
- Loss to follow up or partial course of ANC visit

3. Analysis population

The intention-to-treat population will include all randomized patients, according to the study arm they were randomized in.

Section 5: Trial population

1. Screening data

The following summaries will be presented for all screened patients: inclusion time frame, number of the screened expecting mothers, number of mothers recruited per month, the reason for non-recruitment. This summary will be presented overall and by study center.

2. Eligibility

Eligibility criteria are presented in the study protocol v1.5.

To summarize, all pregnant women >18 years old, with gestational age < 27 weeks and attending ANC care in any of the study centers is eligible to the study

3. Recruitment

The "CONSORT" diagram comprising the number of people screened, eligible, consented, randomized, receiving their allocated intervention (malaria diagnostic and treatment) and followed to delivery will be presented with the study results.

4. Withdrawal/Follow-up - level of withdrawal

The level of consent withdrawal will be tabulated (classified as "consent to continue follow-up, sample and data collection" "consent to continue follow up and data collection", "complete –no further follow-up or

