data collection", "lost to follow up". This will be presented in CONSORT diagram format rather than as a table, with numbers and reasons for withdrawal and/or exclusion from the analysis given at each stage. The numbers (with reasons) of losses to follow-up (dropouts and withdrawals) over the course of the trial will be summarized by treatment arm.

5. Population and subgroup to be analyzed

Intention-to-treat (ITT): All randomized study subjects. This will be the primary population for the analysis.

Per Protocol (PP): All randomized study subjects completing the whole study period (complete cases). For a specific analysis, study subjects with missing data on any of the variables in the model will be excluded from the analysis. Analyses of this population is seen as a sensitivity analysis to investigate whether conclusions are sensitive to assumptions regarding the pattern of missing data

We will analyze independently the following subgroups (Both ITT and PP populations):

- a. Primiparous mother
- b. **Asymptomatic malaria**: women who did not present symptom at any ANC visit but were detected positive for *Plasmodium* spp infection by any diagnostic method.
- c. **Sub microscopic malaria**: any women diagnosed positive for malaria by molecular method (LAMP or post hoc gold standard RT-qPCR)
- d. Malaria species identified: *P. falciparum*, *P. vivax* and mixed infections (3 subgroups)
- e. Women presenting positive malaria testing in placental blood at delivery
- f. Women from newborn with Low Birth Weight

6. Baseline patient characteristics

Expectant women will be described with respect to age, parity, gestity, gestational age, history of malaria, pregnancy complication, both overall and separately for the two randomized groups. These data will be summarized in a table.

Section 6: Analysis

1. Outcome definition

Primary study outcomes are related to newborn health: fetal anemia (hemoglobin <12.5 g/dL), mean birthweight, low birthweight (<2500 g), mean gestational age, preterm delivery (<37 weeks' gestation), mean birthweight for gestational age (Z scores), small for gestational age, fetal loss (spontaneous abortion at <28 weeks' gestation or stillbirth), and the composite outcomes of adverse livebirth (preterm, low

birthweight, or small for gestational age) and adverse pregnancy (adverse livebirth or fetal loss). Mortality outcomes included neonatal, perinatal, and mortality up to age 4 weeks.

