Relative risk (RR) and corresponding 95% confidence intervals (CIs) of adverse birth outcomes and adverse pregnancy based on malaria status will be calculated using log-binomial regression with a log link function. We will use a multivariable quantile regression to further assess the effect of malaria infection on birth weight and gestational age at delivery. Multivariable models will be adjusted for co factors. Adjusters will be included in multivariable analyses based on an a priori hypothesized relationship with the outcome of interest and will be further considered if they had a p < 0.05 in bivariate analysis. No variables chosen as adjusters by substantive knowledge will be excluded based on the results of bivariate analysis. Ultimately, all variables included in the models, including those identified by bivariate screening, will be chosen among variables documented as risk factors for adverse birth outcomes and related to MIP.

3. Missing data

We will use simple imputation for missing covariates (<1%). For outcome variates, we will no implement imputation.

For birth weight, correction factors will be implemented for those collected outside of the study framework.

4. Additional analyses

N/A

5. Harms

6. Statistical software

The data entry is performed using RedCap. Data are exported in STATA and CSV format for analysis in Stata and R.

7. References

Statement references

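### The planned missing-data sensitivity analysis (the per-protocol set) contains no woman without a birth weight, so it cannot test the effect of missing low-birth-weight outcomes

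*SAP*

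**What the plan says.** SAP 5.5 defines the intention-to-treat (ITT) set as "All randomized study subjects. This will be the primary population for the analysis". It defines the per-protocol (PP) set as "All randomized study subjects completing the whole study period (complete cases", and drops from any given analysis a woman who lacks a variable in the model. It then calls the PP analysis a "sensitivity analysis to investigate whether conclusions are sensitive to assumptions regarding the pattern of missing data".

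SAP 6.3 applies simple imputation to covariates, expected to be under 1% missing, and says of outcomes: "For outcome variates, we will no implement imputation".

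Missing weights are foreseen. SAP 4.2 states: "Nonadherence is defined by the number of missed visits, the loss to follow-up or the absence of recorded birth weight". The sample size in SAP 3.3 allows for 20% attrition.

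Other provisions come near the problem:
- SAP 6.3: "For birth weight, correction factors will be implemented for those collected outside of the study framework".
- SAP 5.4: "losses to follow-up (dropouts and withdrawals) over the course of the trial will be summarized by treatment arm".
- SAP 6.1: fetal loss, and an adverse-pregnancy composite that includes it, are outcomes.

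SAP 6.4, on additional analyses, is marked not applicable. Protocol 5.8 gives no method for missing data.

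**The concern.** A sensitivity analysis for missing outcomes has to change what is assumed about the women whose outcome was not seen. Moving from ITT to PP does not. It removes further women whose weight is known and leaves the assumption about the unknown weights as it was.

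LBW is the outcome on which the trial is powered. Loss before delivery could depend on the outcome, or differ by arm, since the arms differ in testing and in the treatment that follows. The table of losses by arm would show an imbalance in numbers but not its effect on LBW. If ITT and PP agree, the SAP as written invites the statement that the result is robust to missing data, when that has not been examined.

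**Working it through.** **Who is in each LBW analysis**

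| Woman | ITT | PP |
|---|---|---|
| Weight recorded, completed, covariates complete | in | in |
| Weight recorded, study not completed | in | out |
| Weight recorded, a covariate imputed | in | out |
| No weight recorded | out (6.3) | out (5.5) |

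The last row is the same in both columns. The comparison can test covariate imputation and the removal of non-completers with a known weight. It cannot test missing weights.

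**The plan's own figure.** Inputs from SAP 3.3 and 4.1: 17.3% vs 12.3%, two-sided 5%, 80% power, 3:1, continuity correction, 20% attrition. The pooled two-proportion formula gives 512 in standard of care (SOC), or 538 with the correction. Then 538 × 4 = 2152, and 2152 × 1.2 = 2582.4, which rounds up to 2583. The stated total is reproduced.

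**Illustration: assumptions**
- A share m of weights is missing, equal in both arms. At m = 0.20 that is 0.20 × 2583 ≈ 517 women.
- Observed LBW is 17.3% (SOC) and 12.3% (intervention).
- Arm sizes are 861/1722 (2:1, SAP 3.2) or 646/1937 (3:1, SAP 3.3). Both are shown because the two sections disagree.

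For each arm, p = (1 − m) × po + m × pm, where po is the LBW rate in observed births and pm the rate in lost births. The test is z = (p_SOC − p_int) / √[p̄(1 − p̄)(1/n_SOC + 1/n_int)], where p̄ is the pooled rate. Set z = 1.96 and solve for pm in the intervention arm.

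Example (3:1, m = 0.20, lost SOC at 17.3%):
- p_int = 0.8 × 0.123 + 0.2 × 0.2144 = 0.1413
- p̄ = (646 × 0.173 + 1937 × 0.1413)/2583 = 0.1492
- SE = √[0.1492 × 0.8508 × (1/646 + 1/1937)] = 0.0162
- z = (0.173 − 0.1413)/0.0162 = 1.96

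This treats filled-in outcomes as if observed. With many imputations and no help from auxiliary variables, the variance per arm is V = p(1 − p)/n + m²[po(1 − po)/(n(1 − m)) + pm(1 − pm)/(nm)], used unpooled. In the same case pm = 0.1881, p_int = 0.1360, SE = √(0.000277 + 0.000079) = 0.0189 and z = 0.0370/0.0189 = 1.96.

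**LBW in lost intervention births at which significance is lost (lost SOC at 17.3%)**

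| Missing | As observed, 2:1 | As observed, 3:1 | Imputation variance, 2:1 | Imputation variance, 3:1 |
|---|---|---|---|---|
| 20% | 22.6% | 21.4% | 20.3% | 18.8% |
| 16.7% | 24.6% | 23.2% | 22.3% | 20.5% |
| 15% | 26.0% | 24.5% | 23.7% | 21.7% |
| 10% | 32.8% | 30.6% | 30.2% | 27.3% |

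The 16.7% row is the loss that 2583 actually covers: (2583 − 2152)/2583 = 431/2583.

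At 20% missing, varying the lost-SOC rate from 5% to 30% moves the as-observed threshold from 11.2% to 34.4% (2:1) or from 10.2% to 33.2% (3:1).

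For comparison, the complete cases alone at 20% missing give a 5.0-point difference: 95% CI 1.7 to 8.3, p = 0.002 (2:1, 689 vs 1378), or 1.4 to 8.7, p = 0.004 (3:1, 517 vs 1550).

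**The case against.** - **The thresholds look closer than they are.** Against lost SOC births at 17.3%, the gap at 20% missing is only 5.3 or 4.1 points (2:1 or 3:1), or 3.0 or 1.5 with imputation variance. Against the intervention arm's own 12.3%, the shift needed is 10.3 or 9.1 points, or 8.0 or 6.5. That is about 1.5 to 1.8 times the observed rate (18.8/12.3 to 22.6/12.3), with lost SOC births unchanged. This stands, and both measures should be read together.
- **20% missing is the unfavourable end.** The stated total allows for 16.7% loss, and nothing says all attrition is missing birth weight. This also stands, which is why lower rates are tabulated.
- **Differential loss is not shown.** Both arms share one visit schedule, and the protocol takes venous blood from SOC women too. The illustration sets loss equal, so it covers outcome-dependent loss only. Loss that differs by arm is possible, but the documents do not establish it.
- **The adverse-pregnancy composite captures one informative reason for a missing weight, known fetal loss.** True, but it does not reach women lost to follow-up.
- **PP is not empty as a check.** Agreed; the point is confined to missing LBW outcomes.
- **The base analysis is partly inferred.** SAP 6.2 frames risk ratios by malaria status; the between-arm ratio is in protocol 5.8. The SAP cites protocol v1.5 and the version available is v1.1, so v1.5 could not be checked. The conflict between SAP 5.5 and 6.3 lies within the SAP itself.

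None of this supplies a test of missing birth weights.

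**Conclusion.** The concern holds. The analysis named as the missing-data check cannot do that job for LBW, and no other planned analysis does. The primary analysis is not invalidated, so this is a change that should be made rather than a fatal fault.

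The likely effect depends on the amount missing. Near 20% the conclusion is fragile: lost intervention births need only moderately exceed lost SOC births in LBW for significance to go. At 10% it is fairly robust, with gaps of 15.5 or 13.3 points (12.9 or 10.0 with imputation variance). These figures rest on equal missingness by arm, observed rates equal to the design rates, and lost SOC births at 17.3%. They illustrate what a proper sensitivity analysis would report and do not predict the trial's result.

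**What to change.** Keep the available-case analysis as primary. In SAP 5.5 and 6.3:

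1. Stop presenting PP as the missing-data sensitivity analysis. Label it a completer analysis, or state whether the treatment deviations in SAP 4.2 exclude women from it.
2. Pre-specify a sensitivity analysis for missing LBW. One option is multiple imputation of birth weight by arm, dichotomised at 2500 g, with a delta-adjusted tipping-point analysis by arm. Predictors can come from data already collected: health centre, parity, gestational age as dated at enrolment (age at delivery is unknown for women lost earlier), maternal hemoglobin, and the malaria results available in that arm. Best-case and worst-case bounds would be simpler but wider.
3. Limit imputation to women eligible for the birth-weight analysis. Protocol 5.8 says: "Mothers with twins will be excluded from the analysis of birth outcomes". Do not impute a weight for a known fetal loss, which is a separate outcome.

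The cost is SAP wording, modest programming and one or two extra tables. No new data and no change to the sample size are needed. It should be fixed before unblinded results are seen, since a method chosen afterwards would carry less weight.
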